### 6.4.5 Data minimisation

We will actively collect data from the eCRF, both retrospectively on patients who have been recruited to the CCP-UK study and prospectively for patients who will be co-enrolled into both ISARIC CCP-UK and CCP-CANCER-UK. The eCRF will obtain clinically specific treatment and stage data that are not available from sources of routine healthcare linkage. Details on existing comorbidities, tumour stage, treatments and clinical outcomes will be collected using linkages to sources of routine healthcare data. Data from these linkages will also give us data not available from the eCRF and allow efficient follow-up. There may be potential overlap between the two data sources. This is justified on the basis of ensuring the most complete coverage possible, in the fastest possible time, as linked data has a delay associated with it. Whilst it would be possible to collect these data in series instead of in parallel, this would take considerably longer, and would give rise to an unacceptable delay in providing our outputs for the benefit of patients, the public, policy makers and clinicians.

### 6.5. Data Management

For the CCP-CANCER UK study the responsibilities for Data Management and monitoring are delegated to the LCTC. A separate Data Management Plan (DMP) will be developed which provides details regarding the internal processes that will be conducted at the CTU throughout the study for data cleaning and monitoring data completion. All data will be managed as per local CTU processes and in line with all relevant regulatory, ethical and legal obligations. No formal study monitoring will be implemented for this study due to the nature of the study, i.e. prospective observational cohort.

The ISARIC CCP-UK data is held in a secure REDCap database at the University of Oxford (data controller for ISARIC CCP-UK data and ISARIC CCP Global data). All data from ISARIC CCP-UK will be securely transferred to the University of Edinburgh (data processor), where the data will be cleaned and NHS/CHI numbers validated using the modulus 11 algorithm. Patients with a cancer diagnosis in the ISARIC CCP-UK dataset, either recorded as a past medical condition or as being on active therapy, will be selected out of the main dataset. This subset will then have all data removed, except for NHS/CHI number, the ISARIC CCP-UK subject identifier number (study number), age and sex. These identifiers will then be securely transferred into the University of Liverpool CCP-CANCER UK study, on a site-specific basis, to allow investigators at each site to complete the data fields for each identified patient. Each site will only be able to see their own data. The University of Edinburgh will integrate data provided by cancer registries, as outlined in the above section, into the data that is uploaded into the Liverpool CCP-CANCER UK REDCap database.

Identifiers in the CCP-CANCER UK REDCap database, will be removed from any data download, leaving only the ISARIC CCP study identifier, which is shared between the ISARIC CCP-UK and CCP-CANCER UK studies. Identifiable data in the CCP-CANCER UK study is only for local investigators to aide recruitment. Once completed, the study data will be checked for accuracy and completeness by the coinvestigators and study management group, then sent securely to

the Scottish National Safe Haven. This will be performed every 3 months, to update the analysis which will be conducted in the Scottish National Safe Haven.

The patient health record will be considered the source document for the study data. No physical study data will exist for any participant – all data will be added to the eCRF directly from the source data for each patient. Data will be stored on the LCTC REDCAP server, data queries will be used to clean the dataset, the data entry/editing for this done by the teams at each site per the CCP Cancer UK study Data Management and Data Query plans.

Data will be transferred to the NHS Scotland National Safe Haven, which is an approved trusted research environment. Data analysts will then access the data through this platform. On this platform, the principal ISARIC CCP-UK study dataset and relevant linked datasets are also held. The National Safe Haven is a secure, firewalled platform that does not have access to the internet. It allows for the secure storage of datasets and analysis within a trusted environment. Access to the National Safe Haven is securely controlled and multifactor authentication steps are in place.

### 6.6. Data protection and Confidentiality

Data collection at sites for this study will be conducted by clinical staff and those involved in the study will ensure that each study participant's privacy and confidentiality is maintained. Participants will not be identified in any published reports of this study. All records will be kept confidential to the extent provided by international and local law. No information concerning the study, or the data will be released to any unauthorized third party.

Data from the CCP-UK study will be processed by the University of Edinburgh. For the purposes of study administration, this permission will be delegated to the University of Edinburgh by delegation from the University of Oxford (ISARIC CCP-UK study data controller). These data, as outlined above, will be processed to allow local investigators to complete additional data fields required by the CCP-CANCER UK study. The data controller for the CCP-CANCER UK study is the University of Liverpool.

For the CCP-CANCER UK study, minimal personal data will be entered into the database for analysis. The patient's identifying personal information (NHS/CHI/HSC number and dates of birth, as well as the ISARIC ID from the main study) will be logged and stored securely. These fields will be marked as identifiers and will not be able to be accessed or downloaded, except by local investigators or individuals with direct purpose for administration of the study. Individuals who are processing this data on behalf of the study will be mandated to complete a minimum level of information governance training, in line with the updated requirements of the GDPR 2018 legislation and amended UK-GDPR 2020 when available. Further research questions, subject to ethical approval, may be answered in retrospect in the future. Since the data generated by this work may be irreplaceable after an outbreak of infectious disease has passed, it is essential that future work is not impeded by unnecessary data loss. The stored research data are therefore likely to be of significant value in the future for other studies and therefore permission is sought for this storing of the research data that does contain minimal patient identifiers such as age, sex and ethnicity.

Data from linkage providers will be provided directly to the Scottish National Safe Haven, which is a secure trusted research environment platform provided by the Edinburgh Parallel Computing Centre (EPCC). This is a secure facility, with full access logging and is only available for the use of pre-approved, bona fide researchers. Multifactor authentication is implemented. Data cannot be removed and there are no outward connections to the internet. Data cannot leave the National Safe Haven without prior review from Public Health Scotland to ensure there are no identifiable data released. This infrastructure is held in a secure facility, details of which cannot be disclosed for operational and security reasons.

• <sup>1 Section 251 (s251) approval and/or applicable application routes in Scotland and Northern Ireland:

## 7. End of Study

The end of the study is defined to be the date on which data for all participants is frozen and data entry privileges are withdrawn from the trial database.

Once there is no need for data collection or cleaning, the identifiable information will be hidden so that no user can access both the study data and patient identifiers. The database will still be pseudo anonymised and possible to link back to the patient if needed.

### 8. Statistical Considerations

#### 8.1. Introduction

Details are provided on the statistical methodology applied to the study design and an overview of the analysis approaches to be taken. Full details of all statistical analyses will be included in separate statistical analysis plans for data from Public Health Wales, and another for other sources.

#### 8.2. Sample Size

As the study does not have a pre-defined hypothesis then no formal power calculations are set. Instead, the study is designed to demonstrate defined, precise set of key parameters used to evaluate the study data. It is anticipated, based on accumulating data from the principal CCP-UK study that a conservative estimate of 5000 cancer patients with COVID-19 will be available. With an estimated fatality rate of 10% then a 95% confidence interval will have an approximate length of 3% (e.g. 8.5% - 11.5%).

In terms of evaluating the difference between prognostic factors, conservative estimates of the precision about an odds ratio are considered for a single binary factor with a 70:30 split in prevalence. Here we would expect that a standard error about a log odds ratio of 0.17 to be observed meaning that an odds ratio <0.84 or >1.19 would be determined statistically significant.

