#### Matched Cohort Study

Using the whole CCP-UK prospective observational cohort, we will perform a matched cohort study. We will match cancer patients and non-cancer patients within the main dataset by age, sex, race and comorbidities. We will determine which factors are associated with fatal outcomes for patients with cancer, particularly with respect to cancer type, stage, immune suppressive or immune modulating/immunotherapy treatment, treatment intent and time from diagnosis.

Data from the CCP-CANCER UK CRF will be supplemented by linked data. Where a data field is discussed that does not appear in the linked data specification, it will be present in the electronic CRF.

We will examine the effects of the following variables on mortality and severity of COVID-19 in cancer patients:

- Age, Sex, Co- morbidities
- Tumour type
- Solid versus haematological malignancy
- Bone marrow transplant
- Stage of malignancy at time of COVID-19 (from CCP-UK CRF) and stage at diagnosis from data linkage.
- \*Diagnosis of malignancy in the last: 1-4 weeks, 1-6 months, 6 months -1 year, 1-5 years, > 5 years
- \*Surgery or Chemotherapy or radiotherapy treatment in the last: 1-4 weeks, 1-6 months, 6 months -1 year,
- > 1 year
- ¥Other systemic anticancer therapy in the last: 1-4 weeks, 1-6 months, 6 months -1 year, > 1 year
- Intent of treatment: Curative vs (neo)adjuvant vs palliative vs watch and wait
- Use of corticosteroids
- Use of Granulocyte colony-stimulating factor

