#### 8.4.4. Analysis of the primary endpoint – patient fatality

The primary endpoint is patient fatality measured as the number of deaths as a ratio of the number of patients with a positive COVID-19 diagnosis. Fatality rates will be displayed overall and within different tumour types as a rate with associated 95% confidence intervals.

Further multivariable logistic regression models will be used to evaluate the risk attributable to key demographic/clinical covariates of interest whilst adjusting for possible confounding factors. Results will be presented in terms of an odds ratio and associated 95% confidence intervals.

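### Section 8.2 calls its odds-ratio precision conservative, but a single unadjusted 70:30 factor is close to the most favourable case, and the printed significance limits are too narrow even for a 50:50 factor

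*Protocol*

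**What the plan says.** Section 8.2 sets no formal power calculation and sizes the study on precision. It expects that "a conservative estimate of 5000 cancer patients with COVID-19 will be available" and takes fatality as 10%. For prognostic factors, it says that "conservative estimates of the precision about an odds ratio are considered for a single binary factor with a 70:30 split in prevalence". From this the section expects "a standard error about a log odds ratio of 0.17 to be observed" and concludes that odds ratios below 0.84 or above 1.19 would be significant. It gives no other scenario and makes no allowance for adjustment.

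The variable list under the Matched Cohort Study heading of section 8.2 includes factors with several levels. One is "Diagnosis of malignancy in the last: 1-4 weeks, 1-6 months, 6 months -1 year, 1-5 years, > 5 years", which has five bands. Two treatment-recency items and treatment intent have four levels each. The list also has yes/no items such as bone marrow transplant and G-CSF use, with no prevalences given.

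Section 8.4.4 states that "multivariable logistic regression models will be used to evaluate the risk attributable to key demographic/clinical covariates of interest whilst adjusting for possible confounding factors", with odds ratios and 95% confidence intervals. Identifying factors associated with poor outcome is the second co-primary objective in section 3.3.

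**The concern.** A conservative precision statement should describe a case at least as hard as most of those to be analysed. For a binary factor the SE is smallest at 50:50 and rises slowly at first as the split becomes less even, so 70:30 is near the bottom of that curve. A factor with several levels spreads the same patients over more cells, and the planned model is adjusted while the calculation is not.

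This is the only precision statement that supports the second co-primary objective. Section 6.4.2 says the study needs to find at what time from diagnosis the risk arises, and it links that to advice on shielding. That question rests on a five-band factor. A reader who relies on section 8.2 would expect tighter intervals there than the sample can give.

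**Working it through.** **Inputs.** N = 5000, fatality p = 0.10 and factor split f = 0.30, all from section 8.2. Section 8.4.3 sets the 0.05 level and section 8.4.4 reports 95% intervals, so z = 1.96.

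**Formula.** With the same fatality in all levels, SE(log OR) = sqrt[(1/n1 + 1/n0) / (p(1−p))]. For a binary factor this equals 1/sqrt[N p(1−p) f(1−f)]. The limits for significance are exp(±1.96 × SE).

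**The plan's own case.** At 70:30 there are 150 deaths among 1500 patients and 350 among 3500.
- SE = sqrt(1/150 + 1/1350 + 1/350 + 1/3150) = 0.103, not 0.17.
- Limits are exp(±1.96 × 0.103) = 0.82/1.22, not 0.84/1.19.
- The two printed figures also disagree with each other: an SE of 0.17 would give limits of 0.72/1.40.
- Both can be recovered as 1.645 × 0.1029 = 0.169 and exp(±0.17) = 0.84/1.19. The 0.17 therefore looks like a one-sided 5% half-width labelled as an SE. That is an inference, but it fits one unadjusted 70:30 factor at N = 5000 and 10% fatality.

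**How favourable is 70:30?** At 50:50 the SE is 1/sqrt(5000 × 0.09 × 0.25) = 0.094, with limits 0.83/1.20. The ratio is sqrt(0.25/0.21) = 1.09. Limits of 0.84/1.19 need an SE of about ln(1.19)/1.96 = 0.089. That is below the 50:50 minimum, so no binary factor reaches them at these inputs.

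**Factors with several levels, without assuming prevalences.** Let the reference level hold a share r of patients. The smallest of the other k − 1 levels holds at most (1 − r)/(k − 1). The least precise contrast with the reference therefore has SE² of at least [1/r + (k − 1)/(1 − r)] / (N p(1−p)). This is smallest at r = 1/(1 + sqrt(k − 1)), which gives SE ≥ (1 + sqrt(k − 1)) / sqrt(450).
- k = 2: 2/21.21 = 0.094, which agrees with the 50:50 value.
- k = 4: 2.732/21.21 = 0.129, upper limit exp(1.96 × 0.129) = 1.29, 25% above the 70:30 SE.
- k = 5: 3/21.21 = 0.141, upper limit 1.32, 37% above the 70:30 SE.

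These are floors. They hold for at least one contrast in each such factor, however patients are distributed. The percentages do not depend on the fatality rate.

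**Illustrations that do rest on assumptions** (the protocol gives none of these prevalences):

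| Case | SE | Limits |
|---|---|---|
| 90:10 | 0.157 | 0.73/1.36 |
| 95:5 | 0.216 | 0.65/1.53 |
| Two of five equal bands, 1000 v 1000 | 0.149 | 0.75/1.34 |

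**Adjustment.** The SE is multiplied by the square root of the variance inflation. An assumed inflation of 2 takes 70:30 to 0.145 (upper limit 1.33) and 90:10 to 0.222 (upper limit 1.55).

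**Higher fatality.** At 20% the upper limit is 1.16 for 70:30 and 1.26 for 90:10. At 30% they are 1.14 and 1.22.

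**The case against.** The strongest reply is that section 8.2 states its scenario openly and sets no power target, and that its printed SE of 0.17 is generous. Taken literally, 0.17 exceeds the four- and five-level floors, the equal-band contrast and the 90:10 case. It covers unadjusted binary factors down to about 8.4% prevalence and, at 70:30, a variance inflation of up to 2.7. This stands as far as the printed SE goes. It does not rescue the printed limits, which are the conclusion the section draws and which fail even at 50:50.

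A second reply is that the word conservative may also reflect the choice of 5000 patients or 10% fatality. More patients or higher fatality would narrow the intervals, and a fatality of about 14% would bring the 70:30 limits to those printed. But the section already calls the 5000 conservative in a separate sentence. The sentence on the odds ratio attaches the word to the precision and names only the factor and its split.

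A third is that a reader might infer that the precision fails for most of the listed factors. The documents do not show this, because no prevalences are given for the binary items. Nor do equal bands follow from the number of bands: five bands imply only that one of them holds 20% or less. A 20% level against all the rest has an SE of 0.118 (limits 0.79/1.26), which is closer to 70:30.

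A reader might also infer that null results will be reported as no excess risk. Nothing in the protocol says so, and section 8.4.4 commits to 95% intervals, which will show any imprecision.

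**Conclusion.** The point holds in a limited form. Describing the odds-ratio precision as conservative is wrong: the case used has an SE 9% above the best possible and no allowance for adjustment. The limits 0.84/1.19 are too favourable for any binary factor at the plan's inputs. Time since diagnosis (five levels), and treatment recency and intent (four levels each), must each contain a level-versus-reference contrast with an SE at least 37% or 25% above the 70:30 value.

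The floors assume N = 5000, the same 10% fatality in all levels, no adjustment, and comparison of each level with one reference level, a coding the protocol does not specify. The size of any further loss from rare factors or adjustment is not fixed by the document. Power figures at a chosen odds ratio would not be a finding against the plan, because the protocol sets no target odds ratio. The defect is in the stated precision. It does not make the sample inadequate.

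**What to change.** In section 8.2:

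1. Correct the 70:30 case to SE 0.103 with limits 0.82/1.22 at two-sided 5%.
2. Delete the word conservative where it describes the odds-ratio precision. Its use for the 5000 patients is a separate matter.
3. Replace the single case with a short table at N = 5000 and 10% fatality. Its rows would be 70:30, 90:10, 95:5 and a pairwise contrast in a five-level factor with equal bands, using the SEs and limits worked out above.
4. Label the prevalences, the equal bands and any variance inflation for adjustment as assumptions.

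No reporting rule for inconclusive factors is needed. It would require an important odds ratio that the protocol does not set, and the confidence intervals are already planned.

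The cost is a few lines of text and a stated precision that is less favourable. No extra patients or data are needed, and the planned analyses do not change.

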#### Co-primary Objectives\*

The co-primary objectives are:

- To determine the COVID-19 fatality rate overall in the cancer population using the most up to date dataset from the first wave
- To identify factors associated with poor outcomes from COVID-19 in patients with cancer.

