### 8.4.3. Levels of Significance

All analyses will be evaluated using the nominal p=0.05 level to determine statistical significance.

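### The odds ratios called significant in Section 8.2 (<0.84, >1.19) lie one stated standard error from 1, not 1.96, and that standard error does not follow from 5000 patients

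*Protocol*

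**What the plan says.** Section 8.2 sets no power calculation and describes the study by its precision instead. It assumes that "a conservative estimate of 5000 cancer patients with COVID-19 will be available". For the first co-primary objective it uses a 10% fatality rate. For prognostic factors it considers "a single binary factor with a 70:30 split in prevalence", calls the estimates conservative, and expects a standard error for a "log odds ratio of 0.17 to be observed meaning that an odds ratio <0.84 or >1.19 would be determined statistically significant".

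Three other places bear on this:

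- Section 3.3 makes this a co-primary objective: "To identify factors associated with poor outcomes from COVID-19 in patients with cancer".
- Section 8.4.3 sets the criterion: "All analyses will be evaluated using the nominal p=0.05 level to determine statistical significance".
- Section 8.4.4, on the logistic models, says: "Results will be presented in terms of an odds ratio and associated 95% confidence intervals".

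The protocol gives no second fatality rate, no variance inflation and no expected loss of patients that would explain the 0.17.

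**The concern.** The standard error, the odds-ratio limits and the significance level should agree with one another, and the standard error should follow from the number of patients, the event rate and the factor split. Neither holds. The limits are what one gets by exponentiating 0.17 itself, with no multiplier for a 5% test. The 0.17 is well above what 5000 patients would give.

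Because the section offers precision in place of power, this sentence is all a reader has for judging what the study can say about prognostic factors. It tells that reader that an observed odds ratio of 1.19 would count as significant. On the protocol's own figures it would not.

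**Working it through.** **Inputs.** n = 5000, fatality 10% and a 70:30 factor (Section 8.2); significance at p=0.05 (Section 8.4.3). The level is taken as two-sided, because limits are given in both directions and 95% intervals are reported.

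**1. Reproducing the printed limits.** exp(−0.17) = 0.844 and exp(+0.17) = 1.185, which round to 0.84 and 1.19. The printed limits are therefore 1 ± one stated standard error on the log scale.

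**2. Limits at p=0.05 if the standard error is 0.17.** exp(±1.96 × 0.17) = 0.717 and 1.395. An observed odds ratio of 1.19 has z = ln(1.19)/0.17 = 1.02, two-sided p = 0.31. This step uses only the stated standard error and significance level, so it holds whatever the sample size or fatality rate.

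**3. Standard error from the section's inputs.** Groups of 3500 and 1500 with 10% fatality give 350 and 150 deaths, and 3150 and 1350 survivors:

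SE = √(1/350 + 1/3150 + 1/150 + 1/1350) = 0.103.

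The equivalent form 1/√(5000 × 0.10 × 0.90 × 0.30 × 0.70) gives the same value. Letting the true odds ratio run from 0.72 to 1.40 with overall fatality held at 10% moves it only between 0.098 and 0.110. The limits are exp(±1.96 × 0.103) = 0.82 and 1.22. An observed odds ratio of 1.19 has z = 0.174/0.103 = 1.69, p = 0.09.

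**4. What a standard error of 0.17 would require.** Any one of these, with the other inputs unchanged:

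- 1/(0.21 × 0.09 × 0.17²) = about 1,831 patients;
- fatality of about 3.4%;
- a factor split of about 8:92;
- a variance inflation of (0.17/0.103)² = about 2.7.

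**5. What limits of 0.84 and 1.19 at p=0.05 would require.** SE = ln(1.19)/1.96 = 0.0888, so about 6,710 patients at 10% fatality.

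**6. Sensitivity to the fatality rate** (5000 patients, 70:30):

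| Fatality | SE | Limits at p=0.05 |
|---|---|---|
| 5% | 0.142 | 0.76, 1.32 |
| 10% | 0.103 | 0.82, 1.22 |
| 15% | 0.086 | 0.84, 1.18 |
| 20% | 0.077 | 0.86, 1.16 |
| 30% | 0.067 | 0.88, 1.14 |
| 50% | 0.062 | 0.89, 1.13 |

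No rate in this range gives a standard error of 0.17.

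**7. Reading 0.17 as a mislabelled half-width.** At 10% fatality, 1.645 × 0.103 = 0.169, which is the half-width of a 90% interval. At 15% fatality, 1.96 × 0.0864 = 0.169, which is the half-width of a 95% interval. A 95% half-width of 0.17 at 10% fatality would need about 7,033 patients.

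**The case against.** The strongest reply is that 0.17 is a half-width with the wrong label, so the limits are about right and only the words standard error are wrong. Step 7 shows this is numerically plausible, and it may well be how the figure arose. But it needs either a 90% interval, which conflicts with Sections 8.4.3 and 8.4.4, or fatality near 15%, which Section 8.2 does not state. The sentence would still need correcting.

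A second reply is that the 10% rate belongs to the preceding paragraph and the odds-ratio paragraph does not repeat it. That is fair: applying it here is an inference. From about 14% upwards (to 50%), 5000 patients would make an observed odds ratio of 1.19 significant. But 10% is the only rate the protocol gives, and step 2 does not depend on it.

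Third, the section calls its estimates conservative, and both complete-case analysis (Section 8.4.2) and covariate adjustment (Section 8.4.4) can enlarge a standard error. That could explain part of 0.17, although a 2.7-fold variance inflation is large and no basis is given. It cannot explain the limits. A cautious standard error should widen them, yet the printed limits are narrower than the uninflated 0.82 and 1.22.

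Lastly, no power calculation is set, 5000 is an estimate of availability, and results will carry their own confidence intervals. All of this stands. It confines the consequence to the stated precision and leaves recruitment and the planned analysis untouched.

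**Conclusion.** The concern holds in both parts.

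The first needs no assumption beyond a two-sided 5% level: a standard error of 0.17 and limits of 0.84 and 1.19 cannot both be right. By the stated standard error, a result with p of about 0.31 is being called significant.

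The second rests on applying the section's 10% fatality to the odds-ratio paragraph. On that basis the standard error is 0.103, not 0.17.

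The size depends on which figure is wrong. If the standard error is recomputed, the limits move modestly, to 0.82 and 1.22. If 0.17 is what was meant, they move substantially, to 0.72 and 1.40. Both describe when an observed odds ratio would reach significance, not an effect detectable with given power. Both come from a single-factor calculation; a multivariable model would generally have a somewhat larger standard error than 0.103.

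**What to change.** Establish what the 0.17 was meant to be, then replace the sentence in Section 8.2 with one of two consistent versions.

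- **Recomputed (preferred).** *With 5000 patients, 10% fatality and a binary factor split 70:30, the standard error of the log odds ratio is 0.10, so an observed odds ratio below about 0.82 or above about 1.22 would be significant at two-sided p=0.05, before adjustment for other covariates.*
- **Keeping 0.17.** State that it is a deliberate inflation for covariate adjustment and missing data, give the basis for it, and print the limits as 0.72 and 1.40.

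If a fatality rate other than 10% was intended for this paragraph, state it and recompute both figures from it.

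The cost is one sentence. No patients, data or analyses change. The stated precision becomes slightly less favourable under the first version and clearly less favourable under the second.
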